We developed a primary care-based intervention called Peer Assisted Lifestyle (PAL) to facilitate delivery of 5As weight management counseling within primary care and increase adoption of intensive VA programs such as MOVE!. The PAL intervention uses a software tool (that we developed) delivered on tablets to facilitate 5As-based weight management counseling with a Veteran health coach and VA PACT healthcare team to promote goal-setting, behavior change, and weight loss in the primary care setting. The PAL intervention also includes up to 12 health coaching calls to patients over 1 year.

As part of a clustered randomized control trial, we will randomize up to 17 PACT teams to either Enhanced Usual Care or the PAL Intervention, recruiting up to 520 subjects.

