To improve counseling opportunities and enhance care coordination during a primary care visit, the VA adopted a patient centered medical home model called Patient Aligned Care Teams (PACT) in 2010. The PACT model provides a team-based, patient-centered approach to health care that utilizes a multidisciplinary practice team that includes a RN Care Manager, a Clinical Associate (LPN), and Administrative Associate, and the primary care provider (the "teamlet") as well as social workers, dietitians, and specialists (other team members) to deliver patient-centered care. This recent implementation of PACT provides the opportunity for longitudinal, team-based care that is integrated with the MOVE! program. However, in the 2013 MOVE! progress report, the majority (55%) of VA sites surveyed reported that MOVE! programs were separate from PACT. Improving weight management counseling by PACT teamlets could increase patient motivation to attend the MOVE! program and facilitate weight loss for those who do not attend.

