#### Project Methods

To achieve these objectives, we will conduct a cluster randomized controlled trial of 17 PACTs (randomized at the provider level) and 520 of their overweight or obese Veteran patients at the Brooklyn campus of the NY Harbor Healthcare System to study the impact of the 12-month PAL intervention when compared to Enhanced Usual Care. Patients in the PAL intervention will complete the GEM tool and receive health coaching, followed by telephone coaching from the health coach over 12 months. The GEM

tool is a mobile-friendly software program designed to be delivered on tablet computers in the clinic setting to assess lifestyle behaviors and barriers, provide tailored advice and patient education materials, create initial weight loss and behavior change goals, and facilitate counseling by the health coach and PACT staff. Patients in the Enhanced Usual Care arm will receive patient education materials (standard VA Healthy Living Messages) and information on the MOVE! program. All patient participants will attend follow-up visits at 6- and 12-months to assess Body Mass Index, waist circumference, blood pressure, diet, blood tests, physical activity, and goal attainment. PACT staff and health coach outcomes will include 5As-related competency, as well as quality and frequency of counseling. If circumstances restrict the availability of in-person visits (e.g. COVID-19) or based on Veteran's preference, this study will provide a remote/tele-visit option for the baseline and follow up visits.

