## DESIGN

Identifying PACT Teams – PACT teams at each site that meet the eligibility criteria below will be selected to be enrolled in the study. Individual PCPs will be allowed to opt out of the study. We do not anticipate that primary care providers will opt out or drop out once enrolled based on the VA PROVE study where all 18 eligible RN care managers and 51/52 PCPs participated for the duration of the study.

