### Exclusion Criteria (note that we are no longer excluding Veterans with specific health issues)

- Non-Veterans
- A documented current history of active psychosis or other cognitive issues via ICD-10 codes
- Has participated in  $\geq 4$  MOVE! sessions in the past year
- Pregnancy

- PCP stating that Veteran should not participate
- Self-reported inability to read at a 5th grade level due to literacy level or vision problems

With an expected 20% participation rate (based on pilot data) and a 75% retention rate (based on rates from another VA study and other technology-based interventions), we will need to screen 2,615 Veterans with overweight/obesity to enroll a baseline sample of up to 520 Veterans and end with 392 Veterans completing the study. With a screening rate of approximately 30-35 Veterans per week (6 women, 24 men), we will be able to recruit our target population by the middle of Year 3 (recruitment will start the first quarter of Year 2).

Study Arms/Randomization – Under the direction of the study statistician, the PACT teams will be randomized at the provider level using a random number generator to either the PAL Intervention or Enhanced Usual Care intervention arms.

- *PAL Intervention group:* Participants will arrive and complete consenting materials, a Baseline Survey, and the GEM tool. They will then have a brief break if needed. After the break, they will work collaboratively with the Health Coach using tool-generated materials to modify their goals into SMART goals (specific, measurable, attainable relevant, and timely). The patient will then receive materials containing an individualized report with a summary of their personalized advice, initial goals, and barriers and facilitators to weight loss. They will also receive a packet of MOVE! handouts tailored to their questionnaire responses and schedule 10-12 follow-up health coaching phone calls during the next 12 months of intervention. The Health Coach will also inform the patient of the resources available to them at the VA (e.g. MOVE, TeleMOVE!) that can assist them in achieving their goals.

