Telephone Coaching/Self-Monitoring Visit – To achieve sufficient intensity according to VA/DOD and USPSTF guidelines, we will incorporate 12 telephone coaching calls by a health coach over 12 months. Scheduled calls will occur two weeks and four weeks post-baseline, then once every month for the remainder of the study. PAL Intervention arm Veterans will receive a reminder call to self-monitor their weight, food intake, and PA for at least 3 days prior to the coaching call. Studies suggest that episodes of short, consistent self-monitoring (for 3 days) lead to weight loss and may promote better adherence. Health coaches will use self-reported self-monitoring data to determine goal adherence and counsel Veterans to encourage small changes. Data from health coaching sessions will be documented in REDCap, our research database. They will help Veterans create new goals when appropriate and use MI techniques to address barriers to behavior change. Veterans will be able to contact health coaches for additional support.

CPRS Research Note/Reminders– The PAL tool creates a provider report that the health coach will cut and paste into CPRS as a research note to summarize and communicate information to the Veteran's PACT team about the health coach session. This note generates a CPRS reminder for the PCP. The reminder facilitates documentation about whether the PACT team discussed goals and provided further counseling. This research note and reminder system will also be used to document both health coach telephone counseling and PACT counseling during future PC visits.

PACT Team Role – PACT teams randomized to the intervention arm will provide at least 3-5 minutes of counseling. They will choose who on the team counsels (based on formative data indicating variability in team member roles). They will document counseling with the help of CPRS reminders, provide brief MI to address barriers (depending on time and Veteran needs), and briefly discuss weight management goals during future PC visits. Each PACT team dietitian will co-sign the health coach CPRS note and will be available as a resource. Health coaches will attend PACT meetings to communicate the progress of enrolled Veterans. They will also communicate PACT team barriers to the PI.

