### 1. Test the impact of the PAL intervention on weight change, clinical, and behavioral outcomes

1a: Veterans in the PAL Intervention arm will lose 2.2 kg and 27% will achieve  $\geq 5\%$  weight loss after 12 months of treatment. There will be 0kg weight change in the Enhanced Usual Care arm, and 12% will achieve  $\geq 5\%$  weight loss.

1b: The PAL Intervention will result in improvements in behavioral outcomes (e.g., increased number of steps, increased fruit/vegetable intake, increased attendance to MOVE!) and clinical outcomes (blood pressure, Low Density Lipoprotein (LDL), Hemoglobin A1C, and waist circumference).

1c: The PAL Intervention will increase attendance to MOVE! and/or other intensive programs.

Method: The primary outcome is mean weight loss at 12 months. Mann-Whitney tests for continuous outcomes (e.g., weight loss) and Fisher's exact tests for categorical outcomes (e.g., whether or not Veterans achieve  $\geq 5\%$  weight loss) will be used to compare the two intervention arms at 12 months, respectively. Unadjusted confidence intervals will be computed to measure the effects of the PAL intervention on the outcomes compared with the Enhanced Usual Care. Repeated measures modeling based on mixed models will be conducted to compare outcome variables between intervention arms, utilizing all of the data at Baseline and at follow-up visits. Such modeling can adjust for baseline characteristics (e.g., diabetes, gender), taking into account: a) the correlation among Veterans within providers, b) the correlation among repeated measures within Veterans. Model-based adjusted confidence intervals will be provided to measure the effects of the intervention on the outcomes as well. Although repeated measures modeling can address missing data automatically, assuming it is missing at random, we will use a multiple imputation procedure to conduct sensitivity analyses under the practical assumption of missing not at random. The sensitivity analyses will be conducted using pattern-mixture models to examine if the statistical findings are robust when considering several scenarios, including the least-favorable scenario where the missing data from the PAL intervention arm were to follow the same pattern as that of the observed data from the Enhanced Usual Care arm.

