Sample Size and Power Analysis – We base our sample size on within-person weight change at Baseline and 12 months in each arm. We assume an interclass correlation coefficient (ICC) of 0.05 for Veterans within each PCP and an ICC of 0.01 for PCPs within each PACT team. Assuming that at the end of the study we have 5 teams in each intervention arm and recruit and obtain baseline data for 52 Veterans per PACT team (392 Veterans total at 12 months), we will have sufficient power to detect a 2.2kg (SD=6.0kg) difference in weight between the intervention and non-intervention arms. If we do not have PACT attrition (5 PACT teams per arm), then we will have additional power. This amount of weight loss is consistent with findings from the ASPIRE VA study and a systematic review of technology-assisted weight loss interventions in primary care. We will also have the power to detect our hypothesized difference of 15% of PAL Intervention Veterans achieving 5% weight loss (clinically significant—as little as 5% weight loss can improve cardiovascular risk), 85% assuming 12% of intervention arm Veterans achieve this amount of weight loss. We will be able to detect 2.9cm change in waist circumference.

If we assume the missing rate at 12 months is 15%, then we will have 44 evaluable Veterans per team. We assume an interclass correlation coefficient (ICC) of 0.03-0.04 for Veterans within each PACT team and an ICC of 0.01 for PCPs within each team. If the ICC of Veterans within each PACT team is 0.03, the power is 85% to detect a 2.2kg (SD=6.0kg) difference in weight between the intervention and intervention arms; the power is 87% to detect a 2.9cm (SD=7.7cm) difference in waist circumference. This amount of weight loss and waist circumference change is consistent with findings from the ASPIRE VA study and a systematic review of technology-assisted weight loss interventions in primary care. In addition, the power is 91% to detect our hypothesized difference between 25% Veterans in the intervention arm and 10% of Veterans in the control arm achieving 5% weight loss (clinically significant). If the ICC of Veterans within each PACT is 0.04, the powers are 81%, 83%, and 87% to detect the same effect sizes of weight loss, waist circumference, and proportion of 5% weight loss, respectively.

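### The plan names both the PACT team and the provider as the allocation unit, and the Aim 1 mixed model omits the team correlation that the power section assumes

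*Combined protocol and SAP*

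**What the plan says.** **Allocation unit.** Four places describe it.

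- Specific Aims: "we will randomize up to 17 PACT teams to either Enhanced Usual Care or the PAL Intervention".
- PAL Intervention Arm, PACT Team Role: "PACT teams randomized to the intervention arm will provide at least 3-5 minutes of counseling".
- Project Methods: "cluster randomized controlled trial of 17 PACTs (randomized at the provider level".
- Study Arms/Randomization (under the Veteran exclusion criteria): "the PACT teams will be randomized at the provider level using a random number generator".

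The first two name the team. The last two name the team and the provider together.

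**Cluster count and structure.** The Sample Size and Power Analysis text assumes 5 teams in each arm at the end of the study. It gives an ICC of 0.05 for Veterans within PCP and "an ICC of 0.01 for PCPs within each PACT team". Its second paragraph, which appears only in the later copy, uses 44 evaluable Veterans per team, an ICC of 0.03 to 0.04 labelled as Veterans within team, and again 0.01 for PCPs within team.

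**Team composition.** The PACT background section describes the teamlet as "a RN Care Manager, a Clinical Associate (LPN), and Administrative Associate, and the primary care provider", with the PCP in the singular. The number of PCPs per team in this trial is not given.

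**Analysis.** The Aim 1 Method lists two sources of correlation for the mixed model: "the correlation among Veterans within providers" and repeated measures within Veteran. Team is not listed. The shorter mixed-model text under Data Analysis, Statistics Analysis, mentions only repeated measures.

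**The concern.** Randomizing teams and randomizing providers are different procedures whenever a team holds more than one PCP, and the power section's ICC for PCPs within team presupposes that it does. The statistician who generates the list cannot tell from the text whether PCPs of one team must go to the same arm.

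The consequence differs by reading. With whole teams allocated, the team is the unit of randomization, and a model that stops at the provider treats PCPs of one team as independent. The standard error is then too small. With PCPs allocated individually, the team effect partly cancels from the comparison, so the provider-only standard error is slightly too large. In that case the worry moves to staff. PAL is delivered partly by the team: staff are trained, the team chooses who counsels, and the team dietitian co-signs notes. Enhanced Usual Care Veterans also follow up with their teamlets. Nothing in the text keeps one team's PCPs in one arm or limits training to PAL teams. The Aim 3 comparison of counselling would be the most exposed.

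**Working it through.** **Assumptions.** Two-sided 5% (the plan states neither alpha nor sidedness), normal approximation, equal cluster sizes. PCPs per team, p, is not in the documents and is varied.

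**1. The plan's own power figures.** Inputs: 2.2 kg, SD 6.0 kg, 5 teams per arm, 44 evaluable per team. Stated power is 85% at ICC 0.03 and 81% at ICC 0.04.

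Design effect DE = 1 + (m − 1) × ICC; effective n per arm = k × m / DE; power = Φ[(2.2/6.0) × √(n/2) − 1.96].

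| Layout per arm | ICC | DE | Effective n | Power | Stated |
|---|---|---|---|---|---|
| 5 teams of 44 | 0.03 | 1 + 43 × 0.03 = 2.29 | 96.1 | 71.9% | 85% |
| 5 teams of 44 | 0.04 | 1 + 43 × 0.04 = 2.72 | 80.9 | 64.5% | 81% |
| 10 clusters of 22 | 0.03 | 1 + 21 × 0.03 = 1.63 | 135.0 | 85.4% | 85% |
| 10 clusters of 22 | 0.04 | 1 + 21 × 0.04 = 1.84 | 119.6 | 80.9% | 81% |

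The literal inputs do not give the stated powers. Treating each team as two independent provider clusters of 22 does. The same layout also matches the stated waist and 5%-weight-loss powers: 87.2% and 90.5% against 87% and 91% at ICC 0.03, and 82.9% and 86.7% against 83% and 87% at ICC 0.04. No other layout tried matched all six. The plan does not state this layout, and its 20 provider clusters do not agree with 17. It does suggest that the calculation used the provider as the cluster, with several PCPs per team and no team correlation.

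Adding the stated 0.01 between two PCPs of a team adds 22 × 0.01 = 0.22 to DE. Power becomes 80.7% (DE 1.85) at ICC 0.03 and 76.4% (DE 2.06) at ICC 0.04.

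**2. Test size of a provider-only model, whole teams allocated.** Inputs: 392 completers in 10 teams, so 39.2 per team and n = 39.2/p per PCP; ICC 0.05 within PCP and 0.01 between PCPs of a team.

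Variance factor the model assumes: A = 1 + (n − 1) × 0.05. True factor: W = A + n × (p − 1) × 0.01. Size = 2 × [1 − Φ(1.96/√(W/A))].

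| p | n | A | W | W/A | Size |
|---|---|---|---|---|---|
| 2 | 19.6 | 1.930 | 2.126 | 1.102 | 6.2% |
| 3 | 13.07 | 1.603 | 1.865 | 1.163 | 6.9% |
| 4 | 9.8 | 1.440 | 1.734 | 1.204 | 7.4% |

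A layout that keeps both counts in the plan, 17 providers in 10 teams (1.7 per team on average), gives the lower end. Per SD², the provider-only variance of an arm mean is 0.05/8.5 + 0.95/196 = 0.01073. With team it is 0.01/5 + 0.04/8.5 + 0.95/196 = 0.01155. The ratio is 1.077 and the size 5.9%.

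**3. Test size if each team's PCPs are split equally between arms.** The team effect cancels, and the true factor is S = A − n × 0.01.

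- p = 2: S = 1.930 − 0.196 = 1.734, ratio 0.898, size 3.9%.
- p = 4: S = 1.440 − 0.098 = 1.342, ratio 0.932, size 4.2%.

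**4. Dilution through shared staff.** This cannot be computed from the documents. They give no PCPs per nurse at this campus, no number of split teams and no rate of spillover.

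**The case against.** The strongest reply is that team and provider are the same thing here. The teamlet description has one PCP, the team eligibility criteria are PCP-level (agreement to take part, panel size), and Project Methods equates 17 PACTs with provider-level allocation. On that reading the four allocation statements agree, no team can be split and no team term is needed. It fails against the power section. An ICC for PCPs within a team is undefined with one PCP per team, 10 teams are not 17, and the stated powers reproduce with two PCP clusters per team. The reply does show that the repair may be mostly clarification.

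A reader might go further and infer that PAL-trained nurses will treat Enhanced Usual Care Veterans, and that this shrinks the 2.2 kg contrast by a definite amount. The documents do not support that. Shared staff are possible, not stated. The remark that "all 18 eligible RN care managers and 51/52 PCPs participated for the duration of the study" concerns another study and does not give PCPs per nurse at this site. The main PAL components (the tool, the coach and the calls) go to individual PAL Veterans. What could spill over is chiefly brief team counselling.

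A reader might also infer that PCPs should be re-allocated in blocks sharing a nurse. That does not follow, and it is costly with few clusters. Using the variances in step 2 and a t-test on cluster degrees of freedom, power for 2.2 kg is 64.8% with 17 providers (15 df) and 56.3% with 10 teams (8 df). Fewer blocks would lower it further.

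Finally, the mixed model should not be called the primary model. The Aim 1 Method names a primary outcome but no primary analysis, and lists the Mann-Whitney test first. That test ignores clustering altogether, which is a larger gap than the missing team term.

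**Conclusion.** The concern stands as an inconsistency in the allocation unit and cluster count, and as a mismatch between the clustering assumed for power and that in the Aim 1 mixed model. If whole teams are allocated, omitting team puts the nominal 5% test at about 5.9% to 7.4%. This rests on the plan's ICCs of 0.05 and 0.01, 10 teams, 392 completers and an assumed range of about 2 to 4 PCPs per team. If teams are split, the omission is mildly conservative (about 3.9% to 4.2%). Dilution through shared staff then becomes a possible problem of unknown size, chiefly for Aim 3. The two harms belong to different allocations and should not be added together. The size error is modest, but it is cheap to remove.

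**What to change.** 1. Reconcile the Specific Aims, Project Methods, Study Arms/Randomization, PACT Team Role and Sample Size text to one allocation unit and one cluster count. Give the number of PCPs per team and say whether staff training is limited to PAL teams.
2. In the Aim 1 mixed model, add a random effect for PACT team beside the provider effect wherever teams hold more than one PCP, with small-sample degrees of freedom. This gives the right error structure whether teams were kept whole or split.
3. Report how many teams have PCPs in both arms, and add a sensitivity analysis restricted to teams wholly in one arm. If allocation has already taken place, keep it and describe it as carried out.

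**Cost.** Protocol and SAP wording, and some precision. With whole teams, the ratios in step 2 make the standard error about 4% to 10% larger (√1.077 = 1.04; √1.204 = 1.10). With 10 teams the t multiplier is 2.31 on 8 df, against 2.13 on 15 df for 17 providers. The sensitivity analysis uses fewer teams and will be less precise.

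### At most 17 providers are allocated with no stated arm sizes or balancing, although the power section assumes equal arms; fixed arms and a constrained draw would be a cheap improvement

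*Combined protocol and SAP*

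**What the plan says.** The Study Arms/Randomization paragraph, which follows the Veteran exclusion criteria, states that the PACT teams are "randomized at the provider level using a random number generator" to one of the two arms, under the direction of the study statistician. Project Methods describes a "cluster randomized controlled trial of 17 PACTs (randomized at the provider level) and 520 of their overweight or obese Veteran patients". The Specific Aims section gives the number as a ceiling: "we will randomize up to 17 PACT teams to either Enhanced Usual Care or the PAL Intervention, recruiting up to 520 subjects". No section states an allocation ratio, block, stratum, matching factor or balance constraint.

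The Sample Size and Power Analysis text, which appears twice, presumes equal arms: "Assuming that at the end of the study we have 5 teams in each intervention arm".

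Provider panels must hold at least 250 patients, with no upper limit. The Statistical and Data Analysis section tests provider and Veteran baseline balance after allocation. Under Aim 1, the Mann-Whitney and Fisher comparisons are unadjusted. The mixed model accounts for correlation within providers and may adjust for baseline characteristics; its two examples, diabetes and gender, are both patient factors. No provider-level covariate is named.

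**The concern.** With so few clusters, the way they are drawn affects the result. A generator that assigns each provider independently can leave the arms clearly unequal in number of clusters. That raises the variance of the treatment effect, whatever number of patients is enrolled. A generator that draws a fixed 8:9 list removes that risk, but can still leave arms whose providers differ in panel size, share of women or typical BMI. A baseline test after allocation cannot correct either problem. The plan leaves open which kind of draw is meant, uses nothing known about the panels to balance the arms, and names no provider-level adjustment for later. At stake are some power in a trial with little to spare, and the credibility of the comparison if the two sets of providers look different.

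**Working it through.** **Inputs.** 17 units (Project Methods). 392 completers, from the recruitment text: "enroll a baseline sample of up to 520 Veterans and end with 392 Veterans completing the study". Difference 2.2 kg and SD 6.0 kg (power section). ICC 0.05 for Veterans within a PCP, or 0.03 to 0.04 for Veterans within a team (both in the power section; the full range is used below). Alpha is not stated; two-sided 0.05 is assumed.

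**1. The plan's own power.** The power section gives 85% at ICC 0.03 and 81% at ICC 0.04, with 5 teams per arm: "If we assume the missing rate at 12 months is 15%, then we will have 44 evaluable Veterans per team". That is 5 × 44 = 220 per arm.

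- ICC 0.03: design effect 1 + 43 × 0.03 = 2.29; effective n = 220/2.29 = 96.1; SE = 6.0 × √(2/96.1) = 0.866; 2.2/0.866 = 2.54; normal-approximation power 71.9%.
- ICC 0.04: design effect 2.72; effective n 80.9; SE 0.943; power 64.5%.

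The stated figures do not follow from the stated inputs. A nested design effect with about 3 PCPs per team comes close (83.8% and 80.9%), but that number is not stated and would mean about 30 PCPs, not 17. This is a separate matter. The steps below use the 17 units and 392 completers.

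**2. Chance of an uneven split, if each of 17 units is assigned independently with probability 1/2.** There are 2^17 = 131,072 equally likely outcomes.

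- 8:9 exactly: 2 × 24,310 / 131,072 = 37.1%
- 6:11 or worse: 43,556 / 131,072 = 33.2%
- 5:12 or worse: 18,804 / 131,072 = 14.3%
- 4:13 or worse: 4.9%

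**3. Cost in power.** Completers per provider m = 392/17 = 23.06. Design effect = 1 + 22.06 × ICC, that is 1.66, 1.88 and 2.10 at ICC 0.03, 0.04 and 0.05. For k1 and k2 providers, SE = 6.0 × √[(design effect/m) × (1/k1 + 1/k2)]. At 8:9 and ICC 0.05 this is 0.880, so 2.2/SE = 2.50. Power is from the noncentral t with 15 df (critical value 2.131).

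| Split | ICC 0.03 | ICC 0.04 | ICC 0.05 |
|---|---|---|---|
| 8:9 | 74.8% | 69.5% | 64.7% |
| 7:10 | 73.6% | 68.3% | 63.5% |
| 6:11 | 71.1% | 65.7% | 60.9% |
| 5:12 | 67.0% | 61.6% | 56.9% |
| Average over independent assignment | 72.2% | 66.8% | 62.1% |

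The losses against 8:9 hardly depend on the ICC: about 1.2 points at 7:10, 3.7 at 6:11 and 7.8 at 5:12, with an average of about 2.6. The variance at 5:12 relative to 8:9 is (1/5 + 1/12)/(1/8 + 1/9) = 1.20.

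**4. Provider-level imbalance with 8:9 fixed.** The standardised difference between arms in a provider-level covariate has SE √(1/8 + 1/9) = 0.486. The chance that it exceeds 0.5 SD in either direction is 2 × [1 − Φ(0.5/0.486)] = 30%.

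To put this on the outcome scale: at ICC 0.05 the between-provider SD of weight change is 6.0 × √0.05 = 1.34 kg. A 0.5 SD gap in a covariate perfectly correlated with the provider effect would move the estimate by 0.67 kg. At an assumed correlation of 0.3 it would move it by 0.20 kg.

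**The case against.** The strongest reply is that nothing here is documented as simple randomisation. A random number generator can just as well shuffle the providers into a fixed 8:9 list, and the equal arms in the power section suggest that this was the intention. This stands: a reader might infer that unrestricted assignment was chosen, but the documents do not say so, and the 33% and 14% apply only if it was. What the text does show is that no restriction is stated.

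A reader might also infer that a trial of this size cannot absorb an unlucky split. The figures do not support that. The commonest uneven split, 7:10, costs about 1 point and the average loss is 2.6 points. Most of the gap below 80% is already there at 8:9 and comes from the number of clusters and the ICC. The table also holds completers per provider constant. If recruitment instead equalised the arms at 196 each (an assumption), power at 5:12 and ICC 0.05 would be about 60% rather than 57%.

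Nor is chance imbalance confounding in the sense of a biased design. Provider-to-provider variation is already in the design effect, so the 30% figure is not an additional loss of power. The mixed model also uses baseline data and can adjust for patient factors, two of which overlap with panel features. It names no provider-level factor, however, and the unadjusted tests have no such protection.

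Finally, it would be wrong to assume that all 17 clusters are known before allocation. The number is a ceiling, PCPs may opt out, and no allocation date is given. The remedy therefore has to depend on timing. Covariate-constrained allocation is also not the only acceptable method; stratifying on panel size with fixed arms would answer much of the point.

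**Conclusion.** The point holds as a moderate and inexpensive improvement to the design. At most 17 providers are allocated by a procedure with no stated arm sizes or balancing, while the power section relies on equal arms.

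If the draw is unrestricted, fixing the arms recovers about 2.6 points of power on average and protects against a 14% chance of losing about 8 points or more. Fixing the arms does not by itself deal with provider-level imbalance, which is the better reason to constrain the draw.

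These sizes rest on 17 providers contributing equally to 392 completers, a two-sided alpha of 0.05 and an ICC of 0.03 to 0.05. The documents do not support saying that simple randomisation was used, that the comparison would be biased, or that an uneven split would by itself defeat the trial.

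**What to change.** **If allocation has not been done:** list the eligible providers who have agreed to take part before drawing. Fix near-equal arms (8:9 if there are 17). Score every allocation on a few panel characteristics, such as number of eligible patients, share of women and mean BMI. Keep a well-balanced subset, for example the best 10%, and draw one allocation from it at random. For 17 providers there are only 24,310 ways to choose the arm of 8, so a short script can list them all. State the ratio and the procedure in the Study Arms/Randomization paragraph. Name the same covariates as fixed terms in the Aim 1 mixed model.

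**If allocation has already been done:** report the method used and the resulting split, and prespecify adjustment for those provider-level covariates in the mixed model before outcomes are examined. The pandemic provisions and a 2022 reference suggest a document amended after the start, so this may be the case that applies.

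**Cost:** a cheap improvement. It needs panel summaries by provider, which should be obtainable from the records system already used to find eligible Veterans, and a short script. The constraining covariates must stay in the analysis model. Each uses one of about 15 provider-level degrees of freedom, so the list should be kept to a few.
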